5.3 Treatment assignment

Not applicable, as this is an open-label trial.

5.4 Treatment blinding

This is an open-label study and treatment blinding is not applicable.

5.5 Treating the patient

5.5.1 Patient numbering

Group 1: Each patient entering this Extension study will continue to be identified by the patient number assigned in the Core study, CZOL446H2337.

Group 2: Patient number consists of a four digit Center number (e.g. 0001) followed by a five digit patient number. The five digit patient number for the first patient starts at 101 (e.g. 00101). Example of patient number in Group 2: 0001_00101.

5.5.2 Dispensing the study drug

Each study site will be supplied by Novartis with study drug in packaging of identical appearance.

The study drug packaging has a 2-part label. Immediately before dispensing study drug to the patient, investigator staff will detach the outer part of the label from the packaging and affix it to the source document (Drug Label Form) for that patient.

5.5.3 Handling of study and additional treatment

5.5.3.1 Handling of study treatment

Study treatment must be received by a designated person at the study site, handled and stored safely and properly, and kept in a secured location to which only the investigator and

designated assistants have access. Upon receipt, all study drugs should be stored according to the instructions specified on the drug labels. Clinical supplies are to be dispensed only in accordance with the protocol.

Medication labels will be in the local language and comply with the legal requirements of each country. They will include storage conditions for the drug, but no information about the patient.

The investigator must maintain an accurate record of the shipment and dispensing of study drug in a drug accountability ledger. Monitoring of drug accountability will be performed by the field monitor during site visits and at the completion of the trial. Patients will be asked to return all unused study drug and packaging at the end of the study or at the time of study drug discontinuation.

At the conclusion of the study, and as appropriate during the course of the study, the investigator will return all used and unused study drug, packaging, drug labels, and a copy of the completed drug accountability ledger to the Novartis monitor or to the Novartis address provided in the investigator folder at each site.

5.5.3.2 Handling of additional treatment

At physician's discretion, vitamin D and calcium supplementation may be managed by diet alone, and this should be recorded in the source records.

When dietary supplements are recommended, this non-study treatment has to be recorded in the Concomitant medications/Significant non-drug therapies of the eCRF specifically:

- Calcium supplements at the time of infusion (all patients)
- Multivitamins that contain the RDA for calcium and vitamin D from Visit 8/8A to Visit 15 in line with [Table 5-1](#)
- Calcium or calcium plus vitamin D supplements from Visit 8/8A to Visit 15 in line with [Table 5-1](#)
- Vitamin D as a single supplement from Visit 8/8A to Visit 15 in line with [Table 5-1](#)

Details are described in the CRF completion guidelines.

5.5.4 Instructions for prescribing and administering study treatment

Patients will receive a single dose of zoledronic acid of 0.05 mg/kg, administered as a slow infusion of 100 ml over 30 minute, at Visit 9 and Visit 12.

AGE	DOSE of ZOLEDRONIC ACID	TIME OF INFUSION
≥ 5 years to 20 years	0.05 mg/kg diluted in 100 ml of normal saline	30 minute infusion

The zoledronic acid dose is not to exceed 5.0 mg.

A peripheral intravenous site must be used for the zoledronic acid 30 minute infusion. The i.v. infusion will be preceded by and followed by a 10 ml normal saline flush of the intravenous line.

As an example, the following table demonstrates how to prepare drug for a patient who weighs 46 kg.

Table 5-2 Preparation of i.v. zoledronic acid infusion

Pt Weight (kg)	Patient dose based on 0.05 mg/kg	Total number of 5.0 mg/100ml vials	Volume of zoledronic acid to add to the normal saline	Volume of normal saline	Total volume of prepared infusion
46 kg	Y = 2.3 mg	1 vial	46 ml	100 ml	146 ml
X kg	X kg * 0.05 mg/kg = Y or Patient dose	1 vial	Y / 5 mg / 100 ml = Patient dose	100 ml	100 ml + volume of reconstituted zoledronic acid to add
Note: The maximum dose is 5 mg therefore the maximum volume from the 5mg/100ml zoledronic acid vial to be used in this study is 100ml					

The investigator should promote compliance by instructing the patient to take the study drug exactly and additional treatment as prescribed and by stating that compliance is necessary for the patient's safety and the validity of the study. The patient should be instructed to contact the investigator if he/she is unable for any reason to take the study drug as prescribed.

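### Protocol 5.5.4 gives two incompatible infusion volumes, the general row of Table 5-2 labels a drug volume as the patient dose, and the Section 3.6 rate example contradicts itself

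*Protocol*

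**What the plan says.** Protocol Section 5.5.4 describes the infusion in three places.

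- The opening sentence says that each dose is "administered as a slow infusion of 100 ml over 30 minute, at Visit 9 and Visit 12".
- The small dose table below it gives "0.05 mg/kg diluted in 100 ml of normal saline", with a 30 minute infusion.
- Table 5-2 is introduced by the words "the following table demonstrates how to prepare drug for a patient who weighs 46 kg". Its worked row has a 2.3 mg dose, 46 ml of drug, 100 ml of saline and 146 ml in total. Its general row gives the total as "100 ml + volume of reconstituted zoledronic acid to add". A note caps the dose at 5 mg and the drug volume at 100 ml.

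The general row first sets "X kg * 0.05 mg/kg = Y or Patient dose", so the patient dose is Y, in mg. In the next calculated column, which is for the volume of drug to add, it prints "Y / 5 mg / 100 ml = Patient dose".

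Two other sections bear on volume and time. Section 3.6 gives an example for a 25 kg child: 100 mL over one hour at 5 mL/minute. Sections 3.3 and 3.6 describe 30 minutes as a minimum, whereas Section 5.5.4 states it as the infusion time.

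**The concern.** This is the operative instruction for preparing a weight-based intravenous drug in children. The general row is the only rule for any child who does not weigh 46 kg. That row uses one term for two quantities in different units. The sentence on administration gives a volume that the table never produces.

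Two things are at stake. The first is delivery: a site that prepares the table's volume but infuses the sentence's volume gives less than the full dose. The second is rate: Section 3.6 itself names fluid overload from too fast an infusion as a risk, so the protocol treats volume and rate as matters of safety.

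There is also a consequence for the data. Protocol Section 9.3 and the SAP section on extent of exposure both summarise infusion volume and duration, and Protocol Section 7.3 has treatment errors recorded. With two stated volumes, the same dose could be recorded as 100 ml or 146 ml, and an error cannot be classified consistently.

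**Working it through.** **Inputs, from Protocol 5.5.4 unless noted.** Dose 0.05 mg/kg, capped at 5 mg. Vial strength 5 mg per 100 ml, that is 0.05 mg/ml, as in the column heading "Total number of 5.0 mg/100ml vials". Saline volume 100 ml. Infusion time 30 minutes. From Section 3.6: 25 kg, 100 mL, one hour, 5 mL/minute.

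**1. Reproduce the worked row.**
- Y = 46 kg × 0.05 mg/kg = 2.3 mg, as printed.
- Drug volume = Y / (5 mg / 100 ml) = 2.3 / 0.05 = 46 ml, as printed.
- Total = 100 + 46 = 146 ml, as printed.
- At the cap, 5 / 0.05 = 100 ml of drug, which agrees with the table's note.

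The table's figures are therefore correct when the vial strength is the divisor.

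**2. Check the label.** The result in step 1 is 46 ml. The cell calls it the patient dose, which the same row defines as Y, here 2.3 mg. The column heading, the worked row and the note all show that a volume is meant.

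**3. Compare the table's total with the 100 ml sentence.** Total = 100 ml + Y / 0.05. The last column assumes a well-mixed preparation of which exactly 100 ml is infused.

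| Weight | Y | Drug volume | Total | Rate over 30 min | Share of dose in 100 ml |
|---|---|---|---|---|---|
| 25 kg | 1.25 mg | 25 ml | 125 ml | 125/30 = 4.2 ml/min | 100/125 = 80% |
| 46 kg | 2.3 mg | 46 ml | 146 ml | 146/30 = 4.9 ml/min | 100/146 = 68% (1.58 mg) |
| 100 kg or more | 5 mg (cap) | 100 ml | 200 ml | 200/30 = 6.7 ml/min | 100/200 = 50% |

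A 100 ml infusion over 30 minutes runs at 100/30 = 3.3 ml/min. The table's total would equal 100 ml only if no drug were added, so the two statements disagree for every patient. In the worked example the gap is 46%.

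**4. Check the Section 3.6 example.**
- 100 mL at 5 mL/minute takes 100/5 = 20 minutes, not one hour, and is shorter than the 30 minute minimum in the same section.
- One hour at 5 mL/minute is 300 mL, not 100 mL.
- 100 mL over one hour is 100/60 = 1.7 mL/minute, not 5.
- Table 5-2 would give this child 125 ml, not 100 mL.

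No pair of the three printed figures agrees with the third.

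**The case against.** The strongest reply is that Table 5-2 is sound and a pharmacist would follow it. The worked row is exact, the note agrees with it, and the dose table's statement about dilution in 100 ml of saline fits a total of 100 ml plus drug. On this view the loose wording within Section 5.5.4 is one sentence. The 30 minute time does not vary within that section, the documents set no rate limit that any rate above exceeds, and the highest rate arises only at 100 kg or more. The missing brackets may also be a product of reading the PDF table as text, since a stacked fraction would flatten to the same string.

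Much of this stands. In particular, a reader might infer from the printed expression that the formula fails to give its own example, because working strictly left to right gives 2.3 / 5 / 100 = 0.0046, apparently 10,000 times too small. The documents do not support that. The table names the vial strength as 5 mg per 100 ml, and with that as divisor the result is 46 ml. The figure 0.0046 is per ml, neither a volume nor a dose, so it cannot be compared with 46 ml. A reader might also infer that one fixed infusion volume ought to be stated. That does not follow either, because the table is built so that the total varies with weight.

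The reply does not remove the conflict over volume. The sentence about a 100 ml infusion is the administration instruction itself, and nothing in the section says that the table overrides it. Nor does it explain the mislabelled cell or the Section 3.6 figures.

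**Conclusion.** The concern holds as a matter of consistency and labelling. The 100 ml sentence and Table 5-2 contradict each other for every patient, by 25 ml at 25 kg, 46 ml at 46 kg and 100 ml at the cap. The drug-volume cell in the general row is mislabelled and its divisor is unbracketed. The Section 3.6 example is internally inconsistent, and 30 minutes is a minimum in some sections and the stated time in another.

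The dose per kg, the cap and the arithmetic of the worked example are not in question. The 68% and 50% delivery figures show what would follow if a site combined the table's preparation with the sentence's volume. They are not evidence that any site did so. No view is taken here on which volume, time or rate is right. The point should be corrected because it sits in the operative preparation instruction, although the worked example limits the risk of miscalculating the dose.

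**What to change.** In the general row of Table 5-2, put the vial concentration in brackets, so that the cell reads as Y divided by (5 mg / 100 ml), and label the result as the volume of drug in ml. Check the typeset table first, in case the brackets or a fraction bar were lost only in text extraction.

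Reconcile the 100 ml sentence in Section 5.5.4, the totals in Table 5-2 and the 25 kg example in Section 3.6 on total volume, time and rate. Say in all places whether 30 minutes is a minimum or the planned time. The sponsor decides the values, and the total may still vary with weight. It would also help for Protocol Section 9.3 and the SAP's extent-of-exposure section to say which volume is summarised.

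The cost is wording in the protocol and one clarifying sentence in the SAP. No sample size, endpoint or model changes.

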5.5.5 Permitted dose adjustments and interruptions of study treatment

Study drug dose adjustments and/or interruptions are not permitted.

5.5.6 Rescue medication

Not applicable.

5.5.7 Concomitant medication

The investigator should instruct the patient to notify the study site about any new medications he/she takes after the start of the study drug. All medications and significant non-drug therapies (including physical therapy and blood transfusions) administered after the patient starts treatment with study drug must be listed on the Concomitant medications/Significant non-drug therapies after start of study drug eCRF.

5.5.7.1 Treatment of study drug related adverse events

As with other bisphosphonates, zoledronic acid has been associated with post-dose symptoms that may include fever, nausea, myalgia, arthralgia and bone pain, with onset occurring within the first 72 hours after the infusion. Typically these symptoms occur with the first infusion of bisphosphonate. The symptoms are usually mild to moderate and rarely severe. These symptoms may be adequately managed, at the discretion of the investigator, with non-steroidal anti-inflammatory agents (e.g. acetaminophen/paracetamol or ibuprofen) and/or anti-

emetics by local treatment standards and according to approved local labeling. Based on data from controlled trials, treatment with non-steroidal anti-inflammatory agents will reduce the incidence of these symptoms by approximately 50%. In managing these symptoms it is important to encourage adequate hydration and food intake. An anti-emetic may be provided to reduce the risk of symptomatic hypocalcemia if the child develops nausea or starts to vomit. Further calcium supplements will be provided for up to 10 days at the time of infusion and parent or legal guardian instructions provided on the signs to watch for as well as an emergency number, if needed.

All dosages prescribed and dispensed to the patient and all dose changes during the study must be recorded on the concomitant medications/significant non-drug therapies eCRF after start of study treatment.

5.5.8 Prohibited medication

Use of the following treatments is NOT allowed throughout the duration of the trial: bisphosphonates, high dose sodium fluoride, denosumab.

5.5.9 Emergency breaking of assigned treatment code

Not applicable in this open-label study.

5.6 Study completion and discontinuation

5.6.1 Study completion and post-study treatment

A patient will be considered to have completed the study when the patient has completed all the assessments in the last visit planned in the protocol (Visit 15, Month 24).

Continuing care should be provided by investigator and/or referring physician based on patient availability for follow-up. This care may include:

- Alternative therapy may be prescribed at the discretion of the treating physician at Visit 15 (EOS).

5.6.2 Discontinuation of study treatment

Discontinuation of study treatment for a patient occurs when study drug is stopped earlier than the protocol planned duration i.e. before Visit 12, Month 18, and can be initiated by either the patient, parent/legal guardian or the investigator.

The investigator must discontinue study treatment for a given patient if he/she believes that continuation would negatively impact the risk/benefit of trial participation.

Study treatment must be discontinued under the following circumstances:

- Patient or parent/legal guardian's wish
- Pregnancy (see [Section 6.5.5](#) and [Section 7.4](#))
- Use of prohibited treatment as per recommendations in [Section 5.5.8](#)
- Any situation in which study participation might result in a safety risk to the patient
- Emergence of the following adverse events:

- ONJ
- Renal failure
- Any laboratory abnormalities that in the judgment of the investigator, taking into consideration the subject's overall status, prevents the subject from continuing participation in the study

If discontinuation of study treatment occurs, the patient should NOT be considered withdrawn from the study. The patient should return to the clinic as soon as possible, after discontinuation of study drug, for a study treatment discontinuation (TD) visit. Treatment discontinuation visit assessments detailed in Visit 15 (Month 24) in [Table 6-1](#) or [Table 6-2](#) should be completed and recorded in the CRF. The investigator must determine the primary reason for the patient's premature discontinuation of study treatment and record this information on the Dosage administration record CRF and the study completion CRF.

After study treatment discontinuation, at a minimum, in abbreviated visits, the following data should be collected at clinic visits or via telephone visits:

- new / concomitant treatments
- adverse events (AEs)/serious adverse events (SAEs)

If the patient, parent/legal guardian cannot or is unwilling to attend any visit(s), the site staff should maintain regular telephone contact with the patient and parent/legal guardian, or with a person pre-designated by the patient or parent/legal guardian. This telephone contact should preferably be done according to the study visit schedule and changes recorded in the relevant pages of the CRF.

[figure not shown]
5.6.3 Withdrawal of informed consent

Patients and/or parents/legal guardians may voluntarily withdraw consent to participate in the study for any reason at any time. Withdrawal of consent (WoC) from the study is defined as when a patient, parent/legal guardian:

- Does not want to participate in the study anymore
and
- Does not want any further visits or assessments
and
- Does not want any further study related contacts
and
- Does not allow analysis of already obtained biologic material

In this situation, the investigator must make every effort (e.g. telephone, e-mail, letter) to determine the primary reason for the patient's or parent's/legal guardian's decision to withdraw his/her consent and record this information.

Study treatment must be discontinued and no further assessments conducted, and the data that would have been collected at subsequent visits will be considered missing.

Further attempts to contact the patient are not allowed unless safety findings require communicating or follow-up.

All efforts should be made to complete the assessments prior to study withdrawal. A final evaluation at the time of the patient's study withdrawal should be made as detailed in [Table 6-1](#) and [Table 6-2](#).

5.6.4 Loss to follow-up

For subjects whose status is unclear because they fail to appear for study visits without stating an intention to discontinue or withdraw, the investigator should show "due diligence" by documenting in the source documents steps taken to contact the subject, e.g. dates of telephone calls, registered letters, etc. A patient cannot be considered as lost to follow-up until the time point of his/her scheduled end of study visit has passed.

5.6.5 Early study termination by the sponsor

The study can be terminated by Novartis at any time for any reason. This may include reasons related to the benefit risk assessment of participating in the study, practical reasons, or for regulatory or medical reasons (including slow enrolment). Should this be necessary, the patient must be seen as soon as possible and treated as a prematurely withdrawn patient. The investigator may be informed of additional procedures to be followed in order to ensure that adequate consideration is given to the protection of the patient's interests. The investigator will be responsible for informing the Institutional Review Board/Independent Ethics Committee (IRBs/IECs) of the early termination of the trial.

6 Visit schedule and assessments

[Table 6-1](#) and [Table 6-2](#) list all of the assessments and indicate with an "X" when the visits are performed.

Patients must be seen for all visits on the designated day, or as close to it as possible. Missed or rescheduled visits should not lead to automatic discontinuation. Patients who prematurely discontinue the study for any reason should be scheduled for a visit as soon as possible, at which time all of the assessments listed for the final visit will be performed. At this final visit, all dispensed investigational product should be reconciled and the adverse event and concomitant medications reconciled on the CRF.

Patients will be contacted for safety evaluations during the 30 days following the last administration of study treatment.

Table 6-1 Group 1 Assessment schedule

	Final visit of Core study		Infusion visit		Tele-phone	Infusion visit		Tele-phone		Notes
Visit	8	8A	9	10	11	12	13	14	15/EOS and TD and/or PSW	Visit 8 is the Core study completion visit. Visit 8A lists the additional assessments which need to be completed for the Extension study. Visits 8 and 8A assessments must be completed on the same day. Visits 8, 8A, and 9 can occur on the same day
Months relative to the Core study (after Visit 9 - Baseline of Extension study)			up to 10 months after V5 (Core study)	10 days after V9	15 (3 months after V9)	18 (6 months after V9)	10 days after V12	21 (9 months after V9)	24 (12 months after V9)	
Obtain informed consent (D) and assent (S)		X								
Inclusion/exclusion criteria (S)		X	X							
Prior/concomitant medications including GCs (D)	X	X	X	X	X	X	X	X	X	
Adverse events (D)	X	X	X	X	X	X	X	X	X	Any AEs that occur after Visit 8 but prior to first dose of Extension study (Visit 9) will be collected on the AE (e)CRF
Vital signs (D)	X		X			X			X	Pulse rate and blood pressure only
Physical examination (S)	X		X			X			X	Including an oral examination for exposed bone
Tanner staging (D), if applicable	X								X	
Weight (D)	X		X			X			X	
Pain assessment	X		X		X	X		X	X	Pain is assessed using Faces Pain Scale-Revised (FPS-R)
Central laboratory test (hematology, biochemistry including urinalysis)	X		X	X		X	X		X	All patients will have limited blood chemistry assessments, GFR and urinalysis performed at

	Final visit of Core study		Infusion visit		Tele-phone	Infusion visit		Tele-phone		Notes
Visit	8	8A	9	10	11	12	13	14	15/EOS and TD and/or PSW	Visit 8 is the Core study completion visit. Visit 8A lists the additional assessments which need to be completed for the Extension study. Visits 8 and 8A assessments must be completed on the same day. Visits 8, 8A, and 9 can occur on the same day
Months relative to the Core study (after Visit 9 - Baseline of Extension study)			up to 10 months after V5 (Core study)	10 days after V9	15 (3 months after V9)	18 (6 months after V9)	10 days after V12	21 (9 months after V9)	24 (12 months after V9)	
										Visit 10 and Visit 13
Serum creatinine (local lab)			X							For exclusion purposes
Ionized calcium (local lab)			X							Measured pre-dose, (local lab) prior to first infusion of Extension study
Bio-markers (Serum P1NP, NTX, BSAP, Trap-5b)	X		X			X			X	Not required at Visit 9 if it occurs within 30 days of Visit 8
Serum 25 hydroxy vitamin D	X		X						X	
Pregnancy Test	X		X		[X]	X			X	To be performed for females with childbearing potential only [Only for sites where additional safeguards are required: Supervised urine pregnancy test]
i.v. drug administration (zoledronic acid)			X			X				
Dispense calcium and vitamin D, if required		X	X			X				
DXA measurements (lumbar spine, total body and distal femur)	X		X			X			X	Not required if obtained 3 months prior to Visit 9
X-ray	X								X	Lateral thoraco-lumbar spine and postero-anterior left hand/wrist
Study completion	X								X	

S = Source data, D = Database, TD = study treatment discontinuation, PSW = premature patient withdrawal

Table 6-2 Group 2 Assessment schedule

	Screening Visit	Infusion Visit ¹		Tele- phone	Infusion Visit		Tele- phone		Notes
Visit	8A	9	10	11	12	13	14	15/EOS and TD and/or PSW	Screening period from Visit 8A to Visit 9 should be as close to 28 days as possible, but cannot be longer than 8 weeks
Months relative to the Core study (after Visit 9 - Baseline of Extension study)		28 days from V8A	10 days after V9	3 months after V9	6 months after V9	10 days after V12	9 months after V9	12 months after V9	
Obtain informed consent (D) and assent (S)	X								
Inclusion/exclusion criteria (S)	X	X							
Medical History (D)	X	X							
Prior/concomitant medication, including GCs (D)	X	X	X	X	X	X	X	X	
Vital signs (D)	X	X			X			X	Pulse and blood pressure
Physical examination (S)	X	X			X			X	Including an oral examination for exposed bone
Tanner staging (D), if applicable		X						X	
Weight (D)	X	X			X			X	
Pain assessment		X		X	X		X	X	Pain is assessed using Faces Pain Scale-Revised (FPS-R)
Central laboratory test (hematology, biochemistry including urinalysis)	X	[X]	X		X	X		X	All patients will have limited blood chemistry, GFR and urinalysis performed at Visit 10 and Visit 13. [Visit 9 lab draw only if more than 4 weeks from Visit 8A].
Serum creatinine (local lab)	X	X							For exclusion purposes
Ionized calcium (local lab)		X							Measured pre-dose (local lab) prior to first infusion

	Screening Visit	Infusion Visit ¹		Telephone	Infusion Visit		Telephone		Notes
Visit	8A	9	10	11	12	13	14	15/EOS and TD and/or PSW	
Bio-markers (Serum P1NP, NTX, BSAP, Trap-5b)		X			X			X	
Serum 25 hydroxy vitamin D	X							X	
Pregnancy Test	X	X		[X]	X			X	To be performed for females with childbearing potential only [Only for sites where additional safeguards are required: Supervised urine pregnancy test]
i.v. drug administration (zoledronic acid)		X			X				
Dispense calcium and vitamin D, if required	X	X			X				
DXA measurements (lumbar spine, total body and distal femur)	X				X			X	
X-ray	X							X	Lateral thoraco-lumbar spine and postero-anterior left hand/wrist
Adverse events and SAEs (D)	X	X	X	X	X	X	X	X	SAEs only collected between Visit 8A and Visit 9 (AEs during this time recorded as medical history)
Study completion								X	
S = Source data, D = Database, TD = study treatment discontinuation, PSW = premature patient withdrawal									

